### **Secondary Analyses Involving Other Markers**

Although our initial genetic hypotheses are focused on the DRD2, we will also use assessments of emotional reactivity to characterize the phenotypes of several other biomarkers that have potential importance for neuroregulatory function and response to pharmacotherapy for smoking cessation. These include: the DRD4, SERT (serotonin transporter), DAT (dopamine transporter) and the NET (norepinephrine transporter). Several exploratory hypothesis are proposed.

We will test the hypotheses that those carrying the long form of the DRD4 (6 repeat or longer) will experience less reactivity during either drug therapy than those homozygous for the short form. We will test the hypotheses that smokers who are heterozygous (S/L) or homozygous (L/L) for the long form of the SERT gene are likely to experience less emotional reactivity in response to nortriptyline therapy vs. either bupropion or placebo.

Polymorphisms of the NET gene have not been extensively characterized in humans and its relationship to antidepressant therapy have not yet been explored. We will evaluate whether or not one the

currently known polymorphisms (1287G/A) is associated with differences emotional reactivity during pharmacotherapy. As a working hypothesis we expect that smokers carrying the GG allele of the 1287G/A variant would be more likely to show reduced emotional reactivity during to nortriptyline therapy vs. bupropion or placebo, in comparison to their GA or AA counterparts, who are not expected to differ in response to the antidepressants.

Each of these genetic markers will be included in the descriptive analysis described above. We will test our exploratory hypothesis by repeating the mixed models analysis described above for our main hypothesis and test for main effects and interactions as we described for the DRD2.

## **E. Human Subjects Research**

### **Protection of Human Subjects**

#### **1. Risks to the Subjects**

**Human Subjects Involvement and Characteristics:** Subjects recruited for this study (N=354) will be current smokers from the Houston metropolitan community. Inclusion criteria are presented in Table 1. All smokers meeting these qualifications will be accepted into the study. Given the nature of the study design it will be necessary to eliminate subjects who do not speak English or have a telephone.

**Sources of Materials:** Participants will be providing physiological data in the form of heart rate, skin conductance, and facial EMG. Participants will also provide several saliva samples for cotinine analysis and a serum blood sample for the use in genetic analyses. Questionnaire data will be obtained that assess previous smoking and health history, mood, attitudes about quitting, coping behavior, and perceived stress. All data will be collected specifically for research purposes and will be coded to maintain confidentiality. The investigations into the genetics of nicotine dependence are just beginning. At present there is no specific disease "risk" information that would require automatic disclosure of the genetic profile to the participants. However, at the conclusion of the laboratory sessions we will share genetic profile information with all interested participants and provide a lay interpretation of the existing literature, with appropriate caveats.

**Potential Risks:** As with most antidepressant medications, bupropion and nortriptyline carry risks of side effects. The typical side effects are not usually serious in nature (e.g., dry mouth, anxiety) and often abate within a few days to weeks after starting medication or once the medication is withdrawn. A detailed description of these effects, are provided below. We will follow the Data and Safety Monitoring procedures for reporting and review of adverse events, approved by MD Anderson for this trial. Participants may also experience tobacco withdrawal effects (e.g., increased irritability, difficulty concentrating, etc.) during smoking cessation. None of these effects typically result in serious adverse health consequences. There are no known risks associated with being subjected to startle probes and picture stimuli. Physiological monitoring carries the minor risk of skin irritation from adhesives, however this reaction is rare and easily treated. It is unlikely that completing questionnaires would lead to any potential risks for participants. In sum, it is highly unlikely that any legal, social, or psychological problems will result from this research.

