**Figure 1 Negative Affect by Genotype and Treatment**

[figure not shown]
abstinence. Smokers carrying the DRD2 A1 allele (A1/A1/A2) quit significantly less often than the homozygous A2s ( $F_{(1,131)}=4.14, p=.04$ ;  $OR=1.82, 95\% CI=1.02, 3.32$ ). This effect was most pronounced during the early weeks of quitting. Moreover, as shown in **Figure 1** we noted a significant pharmacogenetic effect of the drug on negative mood while quitting. Smokers absent the A1 allele (A2/A2) responded to the drug with a substantial reduction in negative affect during the entire post-quitting period for which it was available ( $F_{(1,130)}=6.71, p=.01$ ). These effects were reversed when the drug was withdrawn. In contrast, smokers carrying the A1 allele, showed no significant reduction in negative mood during drug therapy. These results are contrary to what we expected, but if the A1 allele is implicated in reduced DA transmission, the results may be due to the relatively weak DA and NA reuptake properties of venlafaxine. While efficacious in the treatment of depression, in comparison to other antidepressants, venlafaxine is almost 5 times less effective than bupropion at DA reuptake, 10 times less effective at NA reuptake inhibition than nortriptyline and is among the least potent inhibitors of serotonin reuptake of all the SSRIs. We [PCP7]conclude that genotype is important for predicting abstinence but

venlafaxine, and likely other drugs in this class (SSRI) are unlikely to be effective for the control of negative affect during cessation, for the A1 smokers. The current study will ascertain whether bupropion (or nortriptyline) can differentially modify emotional reactivity of A1 or A2 smokers trying to quit, and whether or not this ultimately leads to a better treatment outcome[PCP8].

[figure not shown]
[figure not shown]

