### **Design Summary**

The main objectives of this study are to assess the effects of bupropion and nortriptyline on smokers' emotional reactivity during a quit attempt, as assessed by startle responding to positive and negative emotional cues, and smoking related stimuli; whether this emotional reactivity predicts time to relapse; and, if genetic differences influence the magnitude of these effects. The present study will use a 3x4x4 repeated measures design, with Group (Bupropion/Nortriptyline/ Placebo) serving as the between groups factor, and Days (days post-quit/laboratory assessments) and stimulus valence (positive, negative, neutral, cigarette) serving as within subject factors. The sample will be stratified for race, gender, previous history of major depression, and the DRD2A1/A2 genotype, since the DRD2 marker is of primary interest. As shown Figure 6, 354 smokers will be exposed to four laboratory assessment sessions over a period of 38 days. Medication will be administered in a blinded fashion. Participants will complete a baseline laboratory session before any treatment begins (while still smoking). Immediately after their baseline laboratory session participants will be randomized into one of the three treatments and begin taking the appropriate medication. After ten days of medication, all groups will quit smoking for the duration of the study. Participants in all groups will also receive a series of in-person smoking cessation counseling sessions, two prior to quitting and five after the quit date, plus a series of telephone counseling calls at selected intervals in between the in-person counseling sessions. After completion of all laboratory and counseling sessions, all participants will return for follow up assessments at 3

months (10 days after medication ends) and 6 months post quit. In addition, telephone assessments of abstinence status will be carried out 2 and 4 months post-quit. A study time line is provided on page 20.

**Subject Recruitment.** Participants who want to quit smoking will be recruited from Houston

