### Laboratory Startle Assessment Sessions

The protocol for the individual laboratory startle assessments will be similar for all four sessions, and is described in **Figure 7**. Each laboratory session will begin at approximately the same time of day for each participant (10-11am). Participants will be asked to limit their intake of coffee (or equivalent) to no more than 1 cup prior to 8:00 am on the day of each laboratory session. Smoking for all groups will be unrestricted prior to

the first (baseline) laboratory assessment session. The first session will be used to assess normal startle responses to affective stimuli prior to any nicotine deprivation or pharmacological treatment. Subsequent sessions will be used to assess the effects of treatment modality (nortriptyline, bupropion, placebo) and genotype on startle responses to affective stimuli during the 28 days following the quit attempt. The target days for these assessments are 2 days post quit (range 1-3 days); 5 days post (range 3-5) and 28 days post-quit (range 26-30). Ranges are provided as in our preliminary studies to accommodate scheduling changes resulting from missed visits or a repeat visit 2 (see abstinence criteria). Moreover, we have extended our final session from 10-14 days in our preliminary study to 28 days in the current proposal to more readily capture medication effects on startle responding about midway through drug treatment and towards the end of the 30-day withdrawal period.

At the beginning of each laboratory session, participants will be asked to complete the WSWS, CES-D, and PANAS, as described above. At the baseline session all participants will be instructed to smoke one cigarette after completing these instruments, to ensure similar conditions of non-deprivation preceding the startle probe trials. This is similar to the procedure used by Tiffany and colleagues and is identical to the baseline session described in our preliminary study.

Within each of the four sessions, smokers will be exposed to 48 startle probe trials. Each trial will involve the presentation of a picture with either positive, negative, neutral emotional content, or a smoking cue, while an acoustic stimulus is administered. Each startle probe trial will involve the assessment of eye-blink magnitude.

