### Participant Compensation

Participants will be paid \$300 for attending all laboratory sessions. Payments will be structured as follows: \$60 per completed laboratory session (\$240 total), \$20 bonus for remaining abstinent at each of the 3 post-baseline sessions[PCP17]. In addition, following all laboratory sessions, participants will be paid \$5 per assessment for providing saliva samples to verify their abstinence.

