have lower reactivity than A1 placebo users[PCP18]. Homozygous A2s are expected to respond similarly to both drugs with higher levels of emotional reactivity being observed for placebo vs. either bupropion or nortriptyline.

This hypothesis will be evaluated using models similar to those described for hypothesis 1, but with the addition of Genotype (A1/A2 or A1/A1 vs. A2/A2) as a term in each model. We will specifically evaluate the main effect of Genotype first, followed by the Genotype X Group interaction (the term of interest). Other interactions involving Genotype with Days and Valence will be explored as described for Models 2 and 3 above. Planned contrasts involving the difference in startle magnitude between each Group condition, within Genotype, will also be carried out.

3. Higher levels of emotional reactivity of smokers at baseline and or during cessation will be inversely related to abstinence at the 3 and 6 month follow-ups.

- 3.1. Two types of analysis will be carried out. Our primary focus will be on predicting days to relapse. For this analysis, startle responses will serve as the independent variable with days to relapse as the dependent measure. The primary analysis will focus on the average startle response from the baseline assessment. In secondary models, average response to each valence will be included as predictors to determine the relative predictive strength of the different valences. Startle response from each of the post-quit assessments will also be examined as time dependent variables to determine if startle responses from the other assessments predicts relapse. Each model will also be evaluated controlling for or not controlling for treatment Group. For this analysis we will use Cox proportional hazards regression. We are also interested in predicting abstinence (yes/no) at the 3 and 6 month follow-up. Therefore we will also use the GLIMMIX Macro from SAS, which is an adaptation of the PROC Mixed procedure for hypothesis 1 and 2 for dichotomous out come variables (abstinence) to test whether startle responses are related to abstinence, modeling baseline, valence and time dependent characteristics of the model in the manner proposed above. Interactions between genotype (DRD2 A1 vs. A2) and startle in the prediction of abstinence, will also be explored using in the separate and combined valence models.

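### Genotype results are offered at the end of the laboratory sessions, inside the relapse follow-up for Hypothesis 3; moving disclosure to after the 6-month visit removes an avoidable source of bias

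*Combined protocol and SAP*

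**What the plan says.** **Disclosure.** Under Sources of Materials (Human Subjects Research, Risks to the Subjects), the protocol states that "at the conclusion of the laboratory sessions we will share genetic profile information with all interested participants" and that staff will "provide a lay interpretation of the existing literature, with appropriate caveats". The same paragraph says that no disease-risk information currently requires automatic disclosure.

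**Timing.** The Design Summary states that "354 smokers will be exposed to four laboratory assessment sessions over a period of 38 days", that is, 10 days before and 28 days after the quit date. The section on laboratory sessions sets the later visits at "5 days post (range 3-5) and 28 days post-quit (range 26-30" days. The Design Summary continues: "After completion of all laboratory and counseling sessions, all participants will return for follow up assessments at 3" months, and again at 6 months. Telephone assessments are added at 2 and 4 months.

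**Outcome.** Under Primary Hypotheses, Hypothesis 3 relates startle (mainly the baseline average) to days to relapse by Cox regression, and to abstinence at 3 and 6 months. The plan adds: "Interactions between genotype (DRD2 A1 vs. A2) and startle in the prediction of abstinence, will also be explored". The listed covariates are ethnicity, age, gender, smoking history and depression history. Neither genotype nor disclosure is among them.

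**Why genotype matters.** Preliminary Studies reports that "Smokers carrying the DRD2 A1 allele (A1/A1/A2) quit significantly less often than the homozygous A2s" (OR 1.82). It also reports that A1 carriers had larger baseline startle responses.

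**The concern.** Telling a participant about a genotype that has been linked to quitting is an exposure, and here it falls between the predictor and much of the outcome. If the information discourages A1 carriers, their later relapse rises. Because the pilot ties A1 to larger startle, some of that excess would appear as a startle-relapse association in the direction Hypothesis 3 predicts. If the information motivates carriers, it would mask a real association.

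Only those who ask are told, so the exposure is self-selected. The available text has no provision to record who was told or when, to censor at disclosure, or to adjust for it. What is at stake is the interpretation of relapse and abstinence after about day 28.

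**Working it through.** **1. Order of events.** The last startle session is at day 28 (range 26-30). Disclosure follows the laboratory sessions. Outcomes are assessed at 2, 3, 4 and 6 months. The timing phrase could mean the end of everyone's sessions, but Participant Compensation says that "following all laboratory sessions, participants will be paid" for saliva samples, which refers to the individual's own follow-up. The per-participant reading is therefore the natural one. On the study-level reading, the last enrollees could still be in follow-up when results are released.

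**2. How much of the outcome comes after day 28.** Inputs: expected day-28 abstinence of 60-75% on placebo and 75-80% on each drug (Abstinence Compliance and Startle Assessments); 6-month abstinence of 34% (averaged from the earlier nortriptyline trial) or about 40% (planning assumption), both under Power. Equal arms are assumed.

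- Day 28, low: (60 + 75 + 75)/3 = 70%. High: (75 + 80 + 80)/3 = 78.3%.
- Net loss after day 28: 70 - 40 = 30 points, to 78.3 - 34 = 44.3 points.
- Share of 6-month non-abstinence arising after day 28, at 40% abstinence and ignoring later re-quitting: (70 - 40)/60 = 50%, to (78.3 - 40)/60 = 64%.
- A1 carriers are 42.6% of smokers (Table 3). If they relapse at the same rate as others, carriers lost after day 28 are 0.426 × 30 = 13 to 0.426 × 44.3 = 19 points of the whole sample, before any reduction for those who decline their results.

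**3. The plan's own power figure.** It gives 80% power for 48% versus 32% with 150 per startle group. Check, two-sided 0.05 with pooled variance under the null:

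- SE0 = √(2 × 0.40 × 0.60/150) = 0.0566
- SE1 = √((0.48 × 0.52 + 0.32 × 0.68)/150) = 0.0558
- z = (0.16 - 1.96 × 0.0566)/0.0558 = 0.88, so power is 81.1%.

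The figure reproduces, and moving disclosure does not change it.

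**4. Illustration of possible bias.** The documents give no uptake, no disclosure effect and no A1 share by startle level, so every input here is an assumption. Suppose startle and genotype have no true effect and abstinence is 40% without disclosure. A fraction u of participants take their results, and only disclosed A1 carriers shift, by d points. Then:

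- A1 minus A2 difference = u × d
- High minus low startle difference = (A1 share in high - A1 share in low) × u × d

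The chance of p < 0.05 is in brackets, with 300 analysed:

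| u | d | A1 - A2 | High - low, A1 53% vs 33% | High - low, A1 63% vs 23% |
|---|---|---|---|---|
| 25% | -5 | -1.3 (5.5%) | -0.25 (5.0%) | -0.5 (5.1%) |
| 50% | -10 | -5 (14%) | -1 (5.4%) | -2 (6.5%) |
| 100% | -10 | -10 (43%) | -2 (6.5%) | -4 (11%) |
| 100% | -20 | -20 (97%) | -4 (12%) | -8 (32%) |

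A genotype contrast is far more exposed than the startle contrast. The startle artefact is 0.25 to 4 points under the moderate link and up to 8 under the strong one, against the 16-point design difference. Within a genotype stratum it is zero in this illustration, because uptake does not depend on startle. A positive d gives the same sizes with the sign reversed.

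**The case against.** - **The message may be mild.** The plan promises caveats, and its own account of the literature is mixed. Background cites two null DRD2 smoking studies and a weak effect on abstinence (p = .1). In the pilot, A1 carriage was unrelated to abstinence status (p = 0.28). The profile also covers several genes. A reader might infer that carriers will be told they have a variant for failing to quit; no such wording is in the documents. This stands, and it is why the effect size is unknown.
- **The interaction analysis.** A reader might infer that the exploratory genotype-by-startle test is directly corrupted. A constant shift in carriers' log-odds of abstinence produces a genotype main effect and no interaction. An interaction is distorted only if the disclosure effect differs by startle level. Hypothesis 3 lists no genotype main effect on relapse, so the largest rates in the table belong to a contrast that is not a stated hypothesis.
- **Repair in analysis.** Genotype is measured in everyone, and adding it to the Hypothesis 3 model closes much of the path from startle through genotype to disclosure. This largely stands. It does not help if interest in the results itself varies with reactivity, and uptake that was never logged cannot be recovered.
- **Scope.** Startle for Hypotheses 1 and 2 is measured before disclosure, and the offer is identical in all arms. This stands.
- **Consent.** The consent pages are not in the text available, so they may state the timing or provide for a log.

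**Conclusion.** The point holds as a cheap improvement that protects the later part of Hypothesis 3. Disclosure is placed before the 2- to 6-month assessments, and no safeguard appears in the available text. On the plan's own expectations, with equal arms, a net 30-44 points of abstinence are lost after possible disclosure. That is how much of the outcome is exposed, not an estimate of bias.

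Disclosure can distort later relapse by genotype and, to a smaller degree, the startle-relapse association. Whether it would, and in which direction, is not in the documents.

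A reader might infer that the trial's main hypotheses are compromised. The documents do not support that: Hypotheses 1 and 2 and relapse before day 28 are untouched. Nor does the large share of calendar follow-up after day 28 measure bias, because that depends on uptake and on the effect of being told.

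**What to change.** 1. In Sources of Materials, replace the present timing with: *after the participant's 6-month follow-up has been completed*. Use the same timing in the consent.
2. Log who received results and on what date.
3. If any disclosure happens earlier, add sensitivity analyses of Hypothesis 3: one with genotype in the model, and one censoring follow-up at the date of disclosure.

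**Cost.** One sentence in the protocol and in the consent, plus a simple log. Sample size and power do not change. Interested participants wait about five months longer (roughly 180 - 28 = 152 days). By the protocol's own account, no risk information requires automatic disclosure.

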#### **2. Adequacy of Protection Against Risks**

**Recruitment and Informed Consent:** Participants will be recruited from the Houston community sample using: (1) mail, public service announcements, media interviews, MD Anderson Internet access, newspaper advertisements, MD Anderson Conquest Magazine; (2) through the MDACC community liaison and outreach offices, sending advertisements and mailers to all affiliated providers on the mailing list. Consent will be obtained at the onset of the orientation/baseline interview. Participants will be provided with a detailed description of the study, information on risks, and on their right to withdraw from the study.

**Protection Against Risks:** Bupropion is an FDA approved medication for smoking cessation and its administration will follow approved guidelines. Nortriptyline is recommended as a second line medication in the Clinical Practice Guidelines for Smoking Cessation. Our procedures closely follow those used in previous clinical trials involving these medications. Our study physician will identify participants who have contraindications for bupropion or nortriptyline use and will monitor participants for adverse reactions while they are on medication.

Given the non-invasive, minimal risk nature of the proposed research, we anticipate that the types of adverse experiences that may occur, if any, will focus on concerns about medication side effects, phlebotomy, the discomfort of nicotine withdrawal, possible distress associated and with sensitive issues arising during data collection. We have taken several steps to minimize these risks, as described below.

